7.6.9. Study Follow-Up

About two weeks after the patient leaves treatment, research staff will contact the participant to determine if they proceeded to the next level of care (i.e., day program, office-based opioid treatment, intensive outpatient program, etc.). Details about the program will be recorded on the CRF. If the participant is unable to be reached after three attempts, research staff shall document on the CRF. No further attempts will be made.

7.6.10. Study Completion

[figure not shown]
The subject is considered to have completed the study after they have worn the Bridge™ device for 5 days.

7.6.11. Study Duration

The study duration for each participant is expected to last about two weeks. The duration of the clinical trial enrollment is expected to last two years.

[figure not shown]
7.6.12. Schedule of Events

Study procedures will be conducted according to the schedule [REDACTED]

Impact of Bridge™ device as a non-pharmacological approach to treat opioid withdrawal in opioid use disorder (OUD) subjects in an inpatient treatment center

DENE0001

7.7. Monitoring Plan

Oversight for this clinical trial is provided by the sponsor, investigators, and local IRBs.

As the sponsor of this clinical investigation, Masimo Corporation is required by 21 CFR Part 812, of the Food and Drug Administration regulations to monitor and oversee the progress of the investigation. The monitor(s) assigned by Masimo Corporation to this task will be trained on departmental Standard Operating Procedures (SOPs) on conduct and monitoring of sponsored studies.

In accordance with good clinical practices guidelines, there will be at least three scheduled monitoring visits to ensure overall regulatory compliance of the study:

- An initiation visit, prior to any participant enrollment to confirm site readiness, and to document training on the study protocol and procedures, and use of equipment,
- At least one monitoring visit during initial enrollment, a visit when approximately 20 subjects have been enrolled, and approximately every 4-6 months thereafter.
- A final close out visit after the last participant had finished the study.

Impact of Bridge™ device as a non-pharmacological approach to treat opioid withdrawal in opioid use disorder (OUD) subjects in an inpatient treatment center

DENE0001

The monitor will contact and visit the investigator and will be allowed, on request, to have access to all source documents needed to verify the entries in the CRFs and other GCP-related documents (IRB approvals, IRB correspondences, and ICFs), provided that participant confidentiality is maintained in agreement with HIPAA regulations. The Investigator will provide the monitor access to all necessary records to ensure the integrity of the data (21 CFR 812).

It will be the monitor's responsibility to inspect the CRFs at regular intervals throughout the study, to verify the adherence to the CIP and the completeness, consistency, and accuracy of the data being entered on them.

During each visit, the monitor will also verify adherence to the inclusion/exclusion criteria, and documentation of SAEs/SADEs and protocol deviations/violations and check the CRF against source documentation.

After each visit, the monitor will provide a monitoring report to the Investigator within four weeks of visit completion. The monitoring report will detail findings and open action items observed during the visit. It is the responsibility of the PI and study coordinator(s) to respond to the findings of the monitoring report and complete any open action items as soon as possible but no later than 60 days of receiving the monitoring report. Any open action items not completed within the time allowed may be sufficient grounds for study site suspension or termination; it will be up to the sponsor to determine whether any incomplete action items are sufficient grounds for suspension or termination.

Depending on the quality of the data and/or changes to factors affecting participant safety, additional monitoring visits may be necessary according at the Sponsor's discretion.

8. STATISTICAL DESIGN AND ANALYSIS

This is a single site, two-arm, prospective, randomized, double-blind, sham-controlled clinical trial. The study's main outcomes are COWS and subjective opiate withdrawal scale (SOWS) scores, measured over 8 time periods: at baseline, 30, 60, 120 minutes, 2nd, 3rd, 4th, and 5th day.

The study design data results in correlated observations will be collected repeated measurements within clusters (i.e., patients). These correlations invalidate the independence assumption in commonly used univariate and multivariate statistical techniques such as t-tests and multiple linear regression. Therefore, the Generalized Estimating Equations (GEE) method was used to estimate the power and sample size, a flexible class of models that account for correlated observations and are a commonly used method for repeated data analysis. This class of model does not require the normality assumption and does not require the full specification of the joint distribution of repeated measurements. Further, the power/sample size for testing the time-averaged difference (TAD) between two means from continuous, correlated data that will be analyzed using the GEE method was calculated. Such data occur in two design types: clustered and longitudinal (repeated measurement). Time-averaged difference analysis is often used when the outcome to be measured varies with time.

The following parameter estimates are required for calculating the power:

1. Alpha (α): The probability of rejecting a true null hypothesis = 0.05
2. δ : The time-averaged difference at which the power is calculated. We estimated that the COWS time average is 2.8 for the Bridge group and 6.8 for the sham group, then $\delta = 4.0$.

The δ of 4.0 was selected such as to be conservative and taking into consideration:

Impact of Bridge™ device as a non-pharmacological approach to treat opioid withdrawal in opioid use disorder (OUD) subjects in an inpatient treatment center

DENE0001

- After the first two hours comfort medications and medication tapers may be administered to the control group thus the COWS score may be reduced
- After three days the withdrawal symptoms are anticipated to abate for both groups

The above rationale was discussed with and supported by Masimo Bridge device and OUD clinical experts.

The power was calculated for various TAD δ values 2.8, 3, 4 and 4.7 (see Figure 3).

3. σ : The standard deviation of a response (COWS): 5.047 (estimated, see Table 2 below).
4. ρ : The base correlation between two responses on the same subject. We used the estimate calculated by the other statistician for the sample size calculation (0.40).
5. The treatment group allocation proportion is the proportion of subjects that are in the treatment group. The proportion is 1:1 (50%)
6. The number of time points at which each subject is measured: 9.
7. The time values represent the proportion of the total study time that has elapsed just before the measurement: 0, 0.003, 0.005, 0.01, 0.021, 0.25, 0.5, 0.75, 1, which are equivalent to: prior to device placement, 20 min, 30 min, 60 min, 120 min, 2nd day, 3rd day, 4th day and 5th day.

Data used for the sample size calculation was abstracted from the article by Adrian Miranda & Taca (2018)⁵.

Table 2. COWS Score Statistics Based on Article by Adrian Miranda & Arturo Taca (2018)⁵

Time (mins)	BRIDGE Group			
	Mean COWS	% Reduction	SD	n
0	20.1	0.0	6.1	73
20*	7.5	62.7	5.9	62
30	4.0	80.1	4.4	73
60	3.1	84.6	3.4	71
120	2.8	86.1	**	
1440 (Day 2)	2.1	89.6	**	
2880 (Day 3)	1.4	93.0	**	
4320 (Day 4)	1.0	95.0	**	
5760 (Day 5)	0.6	97.0		33
Average	2.8	86.0		
Pooled SD		5.047		

* 20 minutes measurement is not included in the study design; it was included from the article to enhance the estimates for the required parameters for the sample size/power calculations.

** The yellow highlighted values are estimated (extrapolated from the available data)

A sample of 32 subjects (16 in each group), each measured 9 times, achieve a power of 0.9068 when using a two-sided Wald test from a GEE analysis to test whether the time-average difference of the Bridge subjects differs from that of the sham subjects by more than 4.0 at a significance level of 0.05. The subjects are randomly split between a

[figure not shown]
Impact of Bridge™ device as a non-pharmacological approach to treat opioid withdrawal in opioid use disorder (OUD) subjects in an inpatient treatment center**DENE0001**

Bridge group and a sham group, with 50% of the subjects assigned to the Bridge group. The residual standard deviation is anticipated to be 5.04729. The measurements of each subject will be made at the following times expressed as proportions of the total study time: 0, 0.003, 0.005, 0.01, 0.021, 0.25, 0.5, 0.75, 1, which are equivalent to: prior to device placement, 20 min, 30 min, 60 min, 120 min, 2nd day, 3rd day, 4th day and 5th day. Missing values are assumed to occur completely at random (MCAR).

Anticipating a 50% drop out and missing COWS evaluation rate, 48 participants (24 in each arm) should be enrolled into the study to guarantee a minimum of 32 participants who complete the COWS evaluation and the study.

Figure 3 below shows the relationships of power and sample size for the various δ s.

Figure 3. Power versus Sample Size for δ of 2.8, 3.0, 4.0 and 4.7

A separate Statistical Analysis Plan has been developed for this study.

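### The stated power of 0.9068 counts nine COWS times, one of them not collected; it should match the scheduled times (0.902 or 0.896), and the plan should say which times the difference of 4.0 averages over

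*Combined protocol and SAP*

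**What the plan says.** Section 8 opens by describing COWS and SOWS as "measured over 8 time periods: at baseline, 30, 60, 120 minutes, 2nd, 3rd, 4th, and 5th day". That is eight times: one before the device and seven after it.

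The list of power inputs further on has a different number: "The number of time points at which each subject is measured: 9". The result is then given as "A sample of 32 subjects (16 in each group), each measured 9 times, achieve a power of 0.9068", for a two-sided Wald test from a GEE analysis of the time-averaged difference. The text that follows does not treat the nine times as a planning device. It says "The measurements of each subject will be made at the following times expressed as proportions of the total study time", and the list runs from before device placement through 20, 30, 60 and 120 minutes to Days 2 to 5.

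The footnote to Table 2 states that the "20 minutes measurement is not included in the study design" and that "it was included from the article to enhance the estimates for the required parameters" used in the sample size and power work.

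On the effect, Section 8 says "We estimated that the COWS time average is 2.8 for the Bridge group and 6.8 for the sham group", a difference of 4.0. It does not say which times that average covers. On variability: "The residual standard deviation is anticipated to be 5.04729". Section 7.2 defines the primary endpoint only as change in COWS. Section 8 closes by referring to a separate SAP, which is not part of the combined document.

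**The concern.** A power statement should describe the measurements that the trial will take. This one counts an assessment that no participant will have. It also counts baseline as if it carried treatment information, although the expected difference there is zero under randomisation.

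Two things are at stake. The smaller is the accuracy of the stated power: extra repeated measures shrink the variance of a subject's mean, so counting too many overstates power. The larger is the definition of the primary comparison. Section 8 lists baseline among the outcome times, and the difference of 4.0 has no stated averaging window. If baseline were analysed as an ordinary outcome time, its zero expected difference would pull the time-averaged difference towards zero.

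**Working it through.** **Inputs, all from Section 8.** Difference δ = 4.0; SD σ = 5.04729; within-subject correlation ρ = 0.40; n = 16 per arm; two-sided α = 0.05.

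**Formulas.** With a constant correlation and m equally weighted times:
- variance factor f = (1 + (m − 1)ρ)/m
- SE = √(σ² × f × 2/n)
- power = Φ(δ/SE − 1.96) + Φ(−δ/SE − 1.96)

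**Step 1: reproduce the plan, then change only m.**

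| Times counted | f | SE | Power |
|---|---|---|---|
| 9 (as in the plan) | 4.2/9 = 0.4667 | 1.219 | 0.9068 |
| 8 (baseline + 7 post-device) | 3.8/8 = 0.4750 | 1.230 | 0.9019 |
| 7 (post-device only) | 3.4/7 = 0.4857 | 1.244 | 0.8955 |

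Nine times gives the stated figure to four decimals. A t-based version (0.888) and serial-correlation versions (0.736 to 0.772 using the stated time proportions, about 0.997 by visit order) do not. So the plan's figure does count all nine times equally.

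**Step 2: which times lie behind the Bridge average of 2.8?** From the means in Table 2:
- eight post-baseline rows, including 20 minutes: 22.5/8 = 2.81
- seven scheduled post-device rows: 15.0/7 = 2.14
- eight scheduled times, with baseline: 35.1/8 = 4.39
- all nine rows: 42.6/9 = 4.73

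Only the first matches 2.8. The average behind δ leaves baseline out, while the power formula counts baseline in.

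**Step 3: which times lie behind the SD?** Pooling the four rows that report an SD and n (0, 20, 30 and 60 minutes): √[(72×6.1² + 61×5.9² + 72×4.4² + 70×3.4²)/275] = 5.04729. The SD therefore rests on a third set of times.

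**Step 4: what happens if baseline stays an ordinary outcome time?** If 4.0 is the post-device difference, the average over eight times is (0 + 7 × 4.0)/8 = 3.5. With SE 1.230, power is 0.812. Conversely, for 4.0 to be the average over all eight times, the post-device difference would have to be 4.0 × 8/7 = 4.57.

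**Step 5: baseline as a covariate, seven post-device times.** Assume equal SDs and a common correlation r between baseline and each post-device score; the documents give no value for r. The factor becomes 0.4857 − r². For r = 0.1, 0.2, 0.3 and 0.4, power is 0.901, 0.919, 0.946 and 0.975. With a t reference and r near zero, the covariate costs about one point (0.863 against 0.875).

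**Step 6: scale.** At seven times, 17 completers per arm instead of 16 gives 0.912.

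**The case against.** The strongest reply is that the count hardly matters and that 0.896 is not the one correct replacement. Much of this stands.

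- **The text alone forces only nine to eight.** Section 8 names baseline among its eight measurement times, and eight times gives 0.902, still above 90%. A reader might infer that 0.896 is the true power. That needs the analysis to use post-device times only, which the protocol does not state and the separate SAP may settle. The Bridge average of 2.8 points that way but does not prove it.
- **The other inputs are uncertain too.** The 0.896 keeps δ and σ, which come from other sets of times. With the seven-row Bridge mean of 2.14 and sham held at 6.8 (an assumption), δ would be 4.66 and power 0.963. Section 8 presents 4.0 as conservative. The correlation matters more than the count: at seven times, an assumed 0.3 gives 0.943 and 0.5 gives 0.843. So 0.902 and 0.896 make the count agree with the design; they are not better forecasts.
- **The 0.812 is conditional.** It needs 4.0 to be a post-device difference and baseline to be kept as an ordinary outcome. The protocol commits to neither.
- **The footnote discloses the 20-minute row.** It does, so nothing is concealed. But it explains borrowing published data to estimate parameters. It does not make a time outside the design into a measurement of each subject, and it contradicts the sentence saying that measurements will be made then.

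The mismatch itself has no answer in the text: on either reading, nine is not the number of times this trial measures COWS.

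**Conclusion.** The point holds as a small correction to a stated figure, together with a definition that is missing. The 0.9068 belongs to nine equally counted times and the trial has eight. Consistent unadjusted figures are 0.902 (0.5 points lower) if baseline is kept and 4.0 already allows for it, or 0.896 (1.1 points lower) for the seven post-device times. Both hold δ = 4.0, σ = 5.04729, ρ = 0.40 and 16 per arm fixed, with a normal reference and constant correlation.

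A reader might infer that the trial is underpowered or its result biased. Neither follows: a shift of about one point shows no bias, and one more completer per arm more than offsets it. Nor do the documents show that power is really about 0.81.

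The mismatch in the count is certain. How baseline enters the analysis is not, and that is the more useful thing to settle.

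**What to change.** In Section 8:

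1. Remove 20 minutes from the number of time points and from the list of times at which subjects will be measured. Table 2 can keep the row as borrowed data.
2. State which times the difference of 4.0 averages over.
3. Restate the unadjusted power to match: 0.896 for the seven post-device times, or 0.902 if baseline is kept and 4.0 already allows for it.
4. Unless the SAP already does so, specify that the primary time-averaged difference is taken over 30, 60 and 120 minutes and Days 2 to 5, with baseline COWS as a covariate. If the SAP already says this, correct only the power statement and refer to the SAP.

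Optional: redraw Figure 3 if it was built on nine times, and give a range for the SD, because Table 2 reports SDs at only two of the seven post-device times and none for sham.

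The cost is a few sentences in Section 8 and at most one in the SAP, best settled before unblinding. Baseline COWS is already collected (Section 7.1), so no participants, visits or staff are added, and enrolment need not change on this account.

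### Stated power of 0.9068 counts 9 measurements where the design has 8 (0.902 on the same Wald test), and section 8 leaves the small-sample form of the GEE test unspecified

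*Combined protocol and SAP*

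**What the plan says.** All of the relevant text is in section 8 (Statistical Design and Analysis) of the protocol.

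- **Level.** Alpha is defined as "The probability of rejecting a true null hypothesis = 0.05".
- **Method.** The nearest the section comes to naming the analysis is the clause "correlated data that will be analyzed using the GEE method was calculated". GEE is preferred partly because "This class of model does not require the normality assumption".
- **Test and power.** The only test named is in the power statement: 32 subjects, 16 per arm, each with 9 measurements, "achieve a power of 0.9068 when using a two-sided Wald test from a GEE analysis". The inputs are a time-averaged COWS difference of 4.0, an SD of 5.04729 and a within-subject correlation of 0.40.
- **Measurements in the design.** The outcomes are "measured over 8 time periods: at baseline, 30, 60, 120 minutes, 2nd, 3rd, 4th, and 5th day". The footnote to Table 2 says that the "20 minutes measurement is not included in the study design" and was kept to improve the parameter estimates.
- **Numbers.** Enrolment is 48 (24 per arm), "to guarantee a minimum of 32 participants who complete the COWS evaluation and the study".
- **Elsewhere.** "A separate Statistical Analysis Plan has been developed for this study". Its text is not in the material reviewed.

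Section 8 does not say whether the GEE standard error is model-based or sandwich, which distribution the Wald statistic is referred to, or whether a small-sample correction applies.

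**The concern.** There are two separate issues.

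First, the power figure describes a schedule that will not be run. The ninth measurement serves to estimate parameters, yet it is also counted as data from each subject.

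Second, the robustness that section 8 claims for GEE is a large-sample property in the number of participants, here 32 to 48. At that size a normal cut-off ignores the fact that the variance is estimated. An uncorrected sandwich variance is also biased low, by a factor of about (n-1)/n per arm. If the primary analysis copied the power calculation in this form, the test would exceed its 5% level and its confidence intervals would be too narrow. If the choice is written down nowhere, it could be made after the data are seen.

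**Working it through.** **Inputs (section 8).** Difference 4.0; SD 5.04729; correlation 0.40; two-sided alpha 0.05; n = 16 per arm for the power statement and 24 per arm enrolled; m = 9 in the calculation and 8 in the design. Exchangeable correlation is an assumption, supported by step 1.

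**1. Reproduce the stated power.** `SE = sqrt(2 × SD² × (1 + (m-1) × 0.40) / (n × m))`.

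- m = 9, n = 16: SE = 1.2190 and 4.0/1.2190 = 3.281. Power with a normal cut-off is 0.9068, an exact match.
- The alternatives do not match. A t reference on 30 df gives 0.8877. AR(1) gives about 0.997 by visit index and 0.736 to 0.772 by the plan's time values.

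The stated figure therefore rests on a normal cut-off, 9 measurements and exchangeable correlation.

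**2. Use the 8 designed measurements.** m = 8, n = 16: SE = 1.2299 and 4.0/1.2299 = 3.252.

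- Normal cut-off: 0.9019.
- t on 30 df: 0.8823.

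Of the 2.45-point gap between 0.9068 and 0.8823, 0.49 point (0.9068 - 0.9019) is the plan's own 9-versus-8 inconsistency. The other 1.96 points (0.9019 - 0.8823) come from changing the reference distribution. With all 24 per arm analysed, t-based power at m = 8 is 0.974.

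**3. Type I error of an uncorrected sandwich z-test.** With equal arms and complete normal data the statistic is `T × sqrt(n/(n-1))`, where T follows t on 2n-2 df. The error is `2 × P(t(2n-2) > 1.96 × sqrt((n-1)/n))`.

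| Per arm | Uncorrected sandwich, z | Unbiased SE, z |
|---|---|---|
| 16 | 6.74% | 5.93% |
| 24 | 6.12% | 5.61% |

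Fitting exchangeable GEE to simulated trials with visit effects (3,000 each) gave 7.1% and 6.3% for the uncorrected test, with a Monte Carlo SE of about 0.5 point.

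**4. Departures from normal, complete data (simulated, 8 visits).**

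- Skewed scores (assumed gamma, shape 2 to 0.5), complete data: 6.0-6.7% at 16 per arm and 5.6-6.1% at 24 per arm.
- 24 per arm with 50% random dropout and partial data kept: 6.4% (normal) and 6.0-6.1% (skewed).
- Kauermann-Carroll variance with a t reference, over the same scenarios: 4.9-5.2% (normal) and 4.2-5.1% (skewed).

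**5. How far the restated power depends on other inputs.**

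- *SD.* Pooling the four SDs printed in Table 2 by n-1 gives sqrt((72×6.1² + 61×5.9² + 72×4.4² + 70×3.4²)/275) = 5.047, so the plan's SD includes the 20-minute row. Without that row it is sqrt((72×6.1² + 72×4.4² + 70×3.4²)/214) = 4.776, and t-based power at m = 8, n = 16 is 0.914.
- *Baseline.* The 8 measurements include one taken before device placement, yet 4.0 is applied to all of them. Table 2's average of 2.8 already leaves baseline out: the eight later means sum to 22.5, and 22.5/8 = 2.81, whereas all nine give 42.6/9 = 4.73. If baseline is assumed to contribute no difference, the average difference is 4.0 × 7/8 = 3.5. t-based power is then 0.786 at SD 5.047 and 0.829 at SD 4.776.

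**6. Interval width.** The ratio `t(0.975, 2n-2) / (1.96 × sqrt((n-1)/n))` is 2.042/1.898 = 1.076 at 16 per arm and 2.013/1.919 = 1.049 at 24 per arm.

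**The case against.** A normal-reference formula is routine for planning, and a power statement does not bind the analysis. Variance estimators and reference distributions are usually specified in a SAP, and section 8 says one exists. This stands. A reader might infer that the primary test will run at 6.7%, but the documents do not say that. The inflation is conditional on an analysis that the supplied text does not commit to.

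The size is also modest. The 16-per-arm case takes the plan's completer minimum as the analysed sample, whereas 24 per arm are enrolled and section 7.6.8 allows data collected before withdrawal to be used. At 24 per arm the excess is about 1.1 points, or 0.6 with an unbiased standard error. COWS means near zero late in Table 2 make skewed scores plausible. Skewness lowers the inflation slightly and makes the corrected test slightly conservative.

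Finally, 0.88 is no more secure than 0.9068 unless its assumptions travel with it: step 5 moves it from about 0.79 to 0.91. That also stands, so any restated figure needs its SD and its treatment of baseline beside it.

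None of this removes the 9-versus-8 mismatch, which lies within section 8 and does not depend on the SAP.

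**Conclusion.** The point holds in a limited form. The stated 0.9068 is for 9 measurements. For the 8 in the design it is 0.902 on the plan's own normal-reference test, with a difference of 4.0, SD 5.04729 and exchangeable correlation of 0.40. The supplied text leaves the variance estimator and reference distribution open. Only if an uncorrected sandwich variance is combined with a normal cut-off does Type I error reach about 6.1% (24 per arm) or 6.7% (16 per arm), for normal and complete data.

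Two stronger readings should be resisted. One is that the trial suffers both an inflated alpha and a power of 0.88. These belong to different tests: the uncorrected z-test has simulated power of about 0.909 at 16 per arm with 8 measurements, and the t-based test that has power 0.882 holds 5%. The other is that the plan's own error costs about 2.5 points of power. Its inconsistency costs about 0.5 point, and the rest follows from choosing a t reference. This point does not overturn the sample size.

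**What to change.** 1. Unless the separate SAP already does so, specify for the primary GEE test of the time-averaged COWS difference a small-sample-corrected sandwich variance (for example Kauermann-Carroll) with a t reference on about N-2 degrees of freedom. Cross-refer to it from section 8.
2. Restate power at 16 per arm for the 8 designed measurements and for the test that will be used: 0.902 for the z-test, or about 0.88 for the t-based test. Say that either figure takes an SD of 5.047 and a difference of 4.0 averaged over all 8 measurements. Add that the SD keeps the 20-minute row (4.776 without it, t-based power about 0.91), and that counting baseline as zero difference (assumed average 3.5) gives t-based power of about 0.79 at SD 5.047.

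The cost is a sentence on the test and a restated power figure with its assumptions. Intervals are about 5% wider at 24 per arm and 8% wider at 16 per arm than uncorrected z intervals. The test is slightly conservative if scores are strongly skewed. No change in sample size is needed on this point.

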4. JUSTIFICATION FOR CLINICAL INVESTIGATION DESIGN PLAN

Opioid addiction is a serious public health issue that negatively impacts many communities around the world. Opioid use (including prescription opioids and heroin) kills many people in the U.S. each year. From 1999 to 2018, opioids were involved in more than 446,000 deaths³, approximately 232,000 of which were the result of overdoses related to prescription opioids.⁴ In 2018, the most recent year for which data is available, approximately 47,000 deaths involved opioids, almost 15,000 of which involved prescription opioids.³

The current standard of care treatment for patients suffering from OUD is participation in a medication assisted treatment (MAT) program. However, one of the obstacles of reaching to an MAT program is the fear of enduring opioid withdrawal symptoms associated with the abrupt discontinuation of opioid use during the detoxification phase. Acute opioid withdrawal is often accompanied by painful, often severe flu-like symptoms including but not limited to sweating, gastrointestinal upset, tremors, anxiety, agitation, insomnia, and joint pain lasting for up to two weeks. Accordingly, voluntary discontinuation by opioid users is a long and challenging process. It has been estimated that less than 20% of the more than two million people suffering from OUD in the U.S. are receiving treatment.⁵

Bridge™, which received FDA clearance in 2017 and aids in relieving opioid withdrawal symptoms, may be the solution to helping individuals who suffer from OUD. A 2018 study by Miranda and Taca,⁵ in a cohort of 73 OUD individuals during the induction phase of opioid withdrawal, demonstrated that Bridge™ reduced acute opioid withdrawal symptoms within 15-30 minutes and provided continuous relief for the duration of five days of device wear. In this study, withdrawal symptom evaluated through comparison of *COWS* scores at various time points after device placement to baseline showed 84.6% reduction in *COWS* after the first hour of Bridge™ use and 97.1% after five days.⁵ By aiding in the reduction of withdrawal symptoms, Bridge™ has the potential to help OUD patients with successfully transitioning away from opioids and into an appropriate treatment plan.

CLINICAL INVESTIGATION PLAN

Impact of Bridge™ device as a non-pharmacological approach to treat opioid withdrawal in opioid use disorder (OUD) subjects in an inpatient treatment center

DENE0001

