7.6.8. Device Removal

Medical staff trained and delegated will remove the Bridge device on Day 6. The device shall be disposed in a Sharps container, in accordance with Masimo's Bridge Device Training program, the Device Instructions for Use (DFU) and Operator's Manual.

If subject requests to remove the Bridge device prior to 5 days, they will be withdrawn from further study assessments and procedures, however their data collected up to the point of withdrawal may still be used for data analysis.

CLINICAL INVESTIGATION PLAN

Impact of Bridge™ device as a non-pharmacological approach to treat opioid withdrawal in opioid use disorder (OUD) subjects in an inpatient treatment center

DENE0001

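### Section 8 plans GEE and assumes missing COWS is completely at random while expecting 50% loss; that is not a safe basis, although the bias depends on how loss differs by arm and on an unnamed working correlation

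*Combined protocol and SAP*

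**What the plan says.** Section 8 (Statistical Design and Analysis) names GEE both for the power calculation and for the analysis of the repeated COWS scores. Power is quoted "when using a two-sided Wald test from a GEE analysis". The paragraph that reports it ends: "Missing values are assumed to occur completely at random (MCAR". Enrolment is then set with the words "Anticipating a 50% drop out and missing COWS evaluation rate", giving 48 enrolled for 32 completers.

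Section 7.6.8 (Device Removal) says of participants who ask for removal before 5 days that "they will be withdrawn from further study assessments and procedures". Data collected up to that point may still be used. Section 7.5.4 allows leavers to be replaced.

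The text available names no working correlation for the analysis, no weighting or imputation, and no sensitivity analysis for missing scores. Section 8 refers to a separate Statistical Analysis Plan, whose text was not among the documents reviewed.

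**The concern.** Unweighted GEE is in general consistent only if missingness is unrelated to the outcome, or depends only on covariates in the model. Here a participant can end scoring by asking for the device to come off, and what is scored is how bad withdrawal feels and looks. Loss related to earlier COWS is therefore plausible. It could also differ by arm, because the protocol expects different symptom courses: "We estimated that the COWS time average is 2.8 for the Bridge group and 6.8 for the sham group".

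If high-scoring sham participants leave, the sham mean is understated and a real effect shrinks. If high-scoring Bridge participants leave, the device looks better than it is. Four of the seven post-device times are Days 2 to 5, where losses accumulate, so at 50% loss the MCAR assumption carries much of that comparison.

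**Working it through.** **Inputs from section 8.** Alpha: "The probability of rejecting a true null hypothesis = 0.05", two-sided. Time-averaged difference 6.8 − 2.8 = 4.0. "The residual standard deviation is anticipated to be 5.04729". Within-subject correlation 0.40, 9 measurements, 16 per arm.

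**The plan's own figures.**
- Pooled SD from the four times in Table 2 with a reported SD before Day 2: √[(72×6.1² + 61×5.9² + 72×4.4² + 70×3.4²)/275] = 5.047, as stated.
- SD of a subject's mean under compound symmetry: 5.04729 × √[(1 + 8×0.40)/9] = 3.448.
- SE of the difference: 3.448 × √(2/16) = 1.219.
- Power: Φ(4.0/1.219 − 1.96) = Φ(1.321) = 0.9068, as stated.

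This figure assumes complete data on 16 per arm, so MCAR does not enter it. It reproduces under compound symmetry; the decaying correlations tried gave 0.74 to 0.997.

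**Amount of loss.** 48 = 32 × 1.5, but 48 × (1 − 0.50) = 24, and 1 − 32/48 = 33%. The stated 50% and the enrolment figure therefore imply different losses. That is a separate matter, but 33% is shown below where it was run.

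**Simulation at trial size.** The dropout mechanisms are assumptions; the documents give none. Settings: 24 per arm, 7 post-device times, Table 2 means, SD 5.047, no true difference, visit and arm terms, robust Wald test, 1,000 runs. Loss starts after 120 minutes and reaches about 50% by Day 5. Log odds of leaving change by 0.3 per COWS point. Under MAR leaving depends on the last observed score; under MNAR it depends on the unseen one. Bias is in sham minus Bridge. Each range covers a true correlation that is constant at 0.40 and one that decays (0.7 per visit step). The exchangeable working correlation was fixed at 0.40.

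| Loss mechanism | Independence: bias; Type I | Exchangeable: bias; Type I |
|---|---|---|
| MCAR | −0.01 to 0.03; 0.053–0.065 | −0.02 to 0.04; 0.048–0.065 |
| MAR, same rule in both arms | −0.03 to 0.01; 0.063–0.068 | −0.02 to 0.02; 0.053–0.064 |
| MAR, score-driven in sham only | −0.44 to −0.53; 0.091–0.094 | −0.03 to −0.07; 0.069–0.074 |
| MAR, opposite directions by arm | −0.80 to −1.06; 0.144–0.191 | −0.01 to −0.19; 0.063–0.068 |
| MNAR, sham only | −0.74 to −0.78; 0.132–0.135 | −0.43 to −0.44; 0.079–0.084 |
| MNAR, opposite by arm | −1.33 to −1.46; 0.292–0.297 | −0.71 to −0.77; 0.120–0.146 |

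Monte Carlo error on a 5% rate is √(0.05×0.95/1000) = 0.007. The exchangeable rates under MAR are therefore hardly distinguishable from those under MCAR. The negative sign is bias against the device; it reverses if high scorers leave mainly from the Bridge arm.

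**Large-sample check.** Settings: 200,000 per arm, arm-by-visit means, 50% loss in each arm, odds of leaving multiplied by 2 to 3 per 5 points. This is milder than the table, where 0.3 per point is e^1.5 = 4.5 per 5 points.
- Independence: bias 0.4 to 0.9. A true 4.0 is returned as 3.2 to 4.9.
- At 24 per arm with SE about 1.05, a bias of 0.4 is a shift of 0.38 SE and gives Φ(−1.58) + Φ(−2.34) = 7% rejection under no effect. A bias of 0.9 is a shift of 0.86 SE and gives about 14%.
- Exchangeable: no bias if correlation really is constant; 0.1 to 0.2 if it decays.
- Generalised least squares with the true covariance: 4.0 and 0.0 returned throughout.
- Same MAR mechanism in both arms, independence: 0.0 to 0.2.

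**Smaller SDs.** Table 2's SD falls to 3.4 by 60 minutes. With SDs of that order later on, independence bias under arm-differing dropout was 0.2 to 0.4 at 50% loss in one run. In another it was 0.1 to 0.4 at 50% and 0.1 to 0.3 at 33%, with exchangeable within 0.03 of zero.

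**The case against.** The strongest reply is that this is a small matter of clarification. Section 8 stresses correlated observations and plans with one common correlation, so an exchangeable working structure is the natural reading, and under MAR its bias was at most about 0.2 points against 4.0. Participants and site staff are blinded, so under no true effect one might expect the same dropout rule in both arms, which does little harm. SD 5.047 includes the baseline spread and is probably too large for Days 2 to 5. The proposed remedy was shown at its best: the true covariance is never known, and an unstructured one needs 7×8/2 = 28 parameters at seven visits.

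All of that stands as a limit on size. It does not make MCAR a sound assumption. The working correlation is not stated, and the result can depend on it. With a real effect the arms' scores differ, so even one common rule removes people unequally.

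Three stronger readings are tempting and not supported:
- A reader might infer that the protocol itself ties leaving to withdrawal symptoms. Section 4 says only that "one of the obstacles of reaching to an MAT program is the fear of enduring opioid withdrawal symptoms", which concerns entering treatment. Section 7.6.8 gives no reason for requested removal. Symptom-related loss is an inference.
- A reader might take the MCAR sentence as the rule for the final analysis. It closes the power paragraph, and the analysis rules may be in the separate SAP.
- A reader might conclude that the treatment difference will be biased and the error rate inflated. The larger figures need an independence working correlation, or MNAR loss, together with COWS-dependent loss that differs by arm.

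**Conclusion.** The concern holds in conditional form and should be acted on; confidence is medium. MCAR is doubtful for participant-driven loss at the anticipated 50% when the outcome is withdrawal severity, and the text available offers no analysis that remains valid if it fails.

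Under assumed arm-differing MAR loss at 50%, the shift in the time-averaged difference is about 0.2 to 0.9 points with working independence; the harshest single setting reached 1.06. Type I error is then roughly 7 to 19% at SD 5.047. With an exchangeable structure the shift is 0 to 0.2 points. The same mechanism in both arms gives little or none. MNAR loss can bias any of these methods, a likelihood model included. The direction depends on which arm loses its high scorers. Every figure rests on dropout mechanisms that the documents neither state nor exclude.

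**What to change.** 1. Replace the MCAR sentence in section 8 with the assumption that scores are missing at random given arm, visit and earlier COWS.
2. Keep the time-averaged contrast, and estimate it from all observed scores of all randomised participants by a method valid under that assumption. Either use a likelihood-based repeated-measures model with arm-by-visit means and a named covariance fallback, or multiply impute by arm before GEE with the working correlation named.
3. Add one tipping-point analysis that worsens unobserved Bridge scores until significance is lost, since neither option in step 2 covers MNAR loss.
4. If the separate SAP already specifies this, align section 8 with it instead.

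The cost is wording and a little more analysis work; the sample size, visits and contrast need not change. The one technical risk is that an unstructured covariance may not converge at 24 per arm. The fallback must be named for that reason, and a compound-symmetry fallback would bring back roughly the 0.1 to 0.2 point exposure of exchangeable GEE if the true correlation decays.
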